4.9.5 Other Safety Assessments

4.9.5.1 Physical Examination

The physical examinations are scheduled at Screening/Baseline visit and will be presented in participant data listing including the body system, result (Normal, Abnormal) and description of abnormal findings.

4.9.5.2 Neurological Examination

The neurological examinations are scheduled at Screening/Baseline visit to assess the normality of body systems under the following categories. The results will be presented in a participant data listing.

- General Category
- Cranial Nerves
- Reflexes
- Plantar Reflex
- Motor System – General Category
- Motor System - Muscle Strength
- Motor System - Muscle Tone
- Coordination/Cerebellar Function
- Sensation - Upper Extremities
- Sensation - Lower Extremities

4.9.5.3 C-SSRS Assessment

The most severe suicidal ideation and most severe suicidal behavior will be summarized descriptively by visit for each treatment cohort and overall under FAS. In addition, the most severe assessments during the treatment period for suicidal ideation and suicidal behavior will be summarized as well, according to the table below which list the ideation and behavior from most severe to least severe.

Suicidal Ideation Severity	Suicidal Behavior Severity

 • Active suicidal ideation with specific plan and intent • Active suicidal ideation with some intent to act, without specific plan • Active suicidal ideation with any methods (not plan) without intent to act • Non-specific active suicidal thoughts 	
 • Completed suicide • Actual attempt • Interrupted attempt • Aborted attempt

Suicidal Ideation Severity	Suicidal Behavior Severity
• Wish to be dead	• Preparatory acts or behavior

All the C-SSRS assessment information collected will be provided in the data listing.

4.9.5.4 Pregnancy Information

If the female participant/female partner of a male participant become pregnant during the study, the pregnancy history and current pregnancy information will be presented in participant data listing.

4.10 Subgroup Analyses of Interest

Not applicable.

5. INTERIM ANALYSIS AND ANALYSIS SEQUENCE

No formal interim analyses are planned. The DSMB will be convened for safety monitoring of this research study.

6. SAMPLE SIZE DETERMINATION

This is a multi-center intermediate-size EAP to provide access to the investigational product, SLS-005. The planned enrollment is about 70 participants at up to 25 sites.

There are no prior human studies directly measuring effect of IV trehalose on motor axonal integrity in ALS individuals. The estimated SD of log-transformed NfL levels in an longitudinal observational study [23] is 0.30 log-pg/mL. Preliminary data [23] on change in NfL levels over 6 months (range 4 to 8 months) among 46 ALS participants provided an estimate of the person-to-person standard deviation on the natural-log scale of 0.30 log-pg/mL.

With 70 participants anticipated in the EAP, the study would have greater than 99% power to detect a 30% decline in NfL levels over 6 months. The study would have greater than 90% power to detect a true decline as small as 12% over 6 months. This power calculation is aligned with the NfL data from a separate published dataset suggesting that using a mean longitudinal Δ NfL in the untreated state of 0.011 log units/month, a sample cohort size of 26 participants (1:1) would provide 90% power at 5% significance level to detect a treatment difference of 0.065 log units/month (estimated SD of 0.048 log units/month), using a 2-sample t-test [24].

7. CHANGES FROM AND ADDITIONS TO METHODS PLANNED IN THE PROTOCOL

The protocol Section 9.0 mentioned: for cohort 2, the TEAEs and biomarker NfL levels data collected during the parent HEALEY ALS Platform Trial Regimen E study will be combined with cohort 2 data in this EAP study for final analyses.

Changes in SAP: this is re-evaluated by sponsor and decided that the Regimen E study data will not be included in the analysis plan provided by Everest. The integration analysis of EAP study and Regimen E study data may be scheduled in-house by sponsor.

9. SUPPORTING DOCUMENTATION

Appendix 1 Schedule of Procedures/Assessments

The schedule of assessments for Cohort 1 is given in Table 7, while the schedule of assessments for Cohort 2 is given in Table 8.

- Participants receive a weekly infusion of SLS-005 for up to 24 weeks. Participants who join from the HEALEY ALS Platform Trial Regimen E OLE may do all infusions at home. Participants who join from the HEALEY ALS Platform Trial Regimen E RCT and/or have not previously received SLS-005 in the HEALEY ALS Platform Trial will complete the first four infusion visits in-clinic, then these participants may be permitted, based on safety and tolerability assessments, to have infusions administered at home. There are 25 infusions over 24 weeks (first infusion occurs at the Screening/Baseline Visit).
- In addition to infusion visits, participants will have three scheduled in-clinic visits at Screening/Baseline, Week 3, and Week 24, and 2 phone call or telemedicine visits at Week 12 and approximately 28 days following the last dose of the investigational medical product.

Table 7 Schedule of Activities – Cohort 1 (Trehalose Naïve Participants)

Activity	Screening/ Baseline Combined ⁷	Week 1, Week 2	Week 3	Week 12	Week 24 or Early Term.	Follow-up Safety Call
	Clinic	In-clinic infusion- only ⁵	Clinic	Telemed/ Phone	Clinic	Telemed/ Phone
	Day -21 to 0	Day 7 ±3, Day 14 ±3	Day 21 ±3	Day 84 ±7	Day 168 ±14	28±7 days after last dose
Written Informed Consent	X					
Inclusion/Exclusion Review	X					
ALS & Medical History	X					
Demographics	X					
Physical Examination	X					
Neurological Exam	X					

Activity	Screening/ Baseline Combined ⁷	Week 1, Week 2	Week 3	Week 12	Week 24 or Early Term.	Follow-up Safety Call
	Clinic	In-clinic infusion- only ⁵	Clinic	Telemed/ Phone	Clinic	Telemed/ Phone
	Day -21 to 0	Day 7 \pm 3, Day 14 \pm 3	Day 21 \pm 3	Day 84 \pm 7	Day 168 \pm 14	28 \pm 7 days after last dose
Vital Signs ¹	X Weekly documentation of infusion-associated vital signs					
Slow Vital Capacity (SVC)	X				X	
ALSFRS-R	X		X	X	X	
ALSAQ-40	X				X	
Clinical Safety Labs ²	X		X		X	
Biomarker Collection (Serum)	X				X	
Concomitant Medication Review	X		X	X	X	
Adverse Event Review	X		X	X	X	X
Document infusion-related adverse events ³	X Weekly documentation of infusion-related adverse events.					
Columbia-Suicide Severity Rating Scale	X		X		X	
Adjust Dose as Needed ⁴			X			
Administer/Dispense Study Drug ⁵	X Weekly infusions will continue through Week 24. Based on safety and tolerability assessments, infusions may be administered at home after the first 4 in-clinic infusions at Screening/Baseline, Week 1, Week 2, and Week 3.					
Drug Accountability/Compliance ⁶	X Weekly infusions will continue through Week 24. Refer to the Pharmacy Manual, site policy, and GCP guidelines on drug accountability, compliance, and source documentation.					
Vital Status Determination ⁸					X	X

¹ Vital signs are collected at the Screening/Baseline, Week 3, and Week 24 visits and weekly in conjunction with study drug administration from Baseline through Week 24. Vital signs collected at in-clinic visits (Screening/Baseline, Week 3, Week 24) include systolic and diastolic pressure, respiratory rate, heart rate, temperature, and weight. Height is measured at Screening/Baseline Visit only. If significant weight change is reported or suspected at any point during the study, the SI may choose to collect an additional in-clinic weight at their discretion. During each weekly infusion, vital signs associated with the infusion (systolic and diastolic pressure, respiratory rate, and heart rate) are to be measured pre-infusion, 30 minutes (\pm 5 mins) after the start of infusion (SOI), 60 minutes after the SOI (\pm 10 mins), and 90 minutes (\pm 10 mins) after the SOI. If a participant requires a 90-minute infusion duration due to receiving more than 2 bags of study drug, an additional vital signs measurement is to be completed approximately 30 minutes (\pm 10 mins) after the end of the 90-minute infusion.

Activity	Screening/ Baseline Combined ⁷	Week 1, Week 2	Week 3	Week 12	Week 24 or Early Term.	Follow-up Safety Call
	Clinic	In-clinic infusion- only ⁵	Clinic	Telemed/ Phone	Clinic	Telemed/ Phone
	Day -21 to 0	Day 7 ±3, Day 14 ±3	Day 21 ±3	Day 84 ±7	Day 168 ±14	28±7 days after last dose

2 Clinical safety labs include hematology (CBC with differential), complete chemistry panel and urinalysis at Screening/Baseline, Week 3, and Week 24. Hb A1C will be included in labs at Screening/Baseline and Week 24. If labs are abnormal at Week 3, they may need to be repeated per investigator judgement. Serum pregnancy testing will occur in women of child-bearing potential at the Screening Visit and as necessary during the study. Pregnancy testing is only repeated as applicable if there is a concern for pregnancy. All urine samples must be collected prior to IP administration. Clinical safety labs may be drawn at the study site or obtained at a local site convenient for the participant. Clinical safety lab results obtained locally may be used to assess participant eligibility.

3 Infusion-related AEs are documented weekly in conjunction with study drug administration from Screening/Baseline through week 24.

4 The weight collected at the Screening/ Baseline clinic visit will be used to calculate the participant's initial dose. The participant will remain on a stable dose until the next in-person visit when weight be collected, at which point the dose may be adjusted if the participant's weight has increased or decreased by 2kg. Additional information on dose adjustments is included in Protocol section 6.7.4 Dosing Changes.

5 Administer first dose of study drug only after Screening/Baseline Visit procedures are completed. For participants in cohort 1, infusions occur in-person at clinic at the Screening/Baseline study visit, Week 1, Week 2, and the Week 3 study visits. Weekly infusions will continue through Week 24. An in-clinic infusion and clinic visit may occur on the same day, provided both visits are conducted in-person and within window. There should be no fewer than 4 days (96 hours) between study drug infusions.

6 Refer to the Pharmacy Manual, site policy, and GCP guidelines on site investigator responsibilities, drug accountability, compliance, and source documentation. Any and all accountability records may be requested by sponsor for review at any time.

7 The combined Screening/ Baseline visit may be split into a Screening and a Baseline visit as needed. If baseline infusion occurs on the same day as screening, it must occur after obtaining written informed consent, completing all screening procedures, and confirming participant eligibility.

8 Vital status, defined as a determination of date of death or death equivalent or date last known alive, will be determined for each enrolled participant at the end of their EAP participation (generally the Week 24 visit, as indicated). If at that time the participant is alive, his or her vital status should be determined again at the time of the last participant last visit (LPLV) of the EAP. We may also ascertain vital status at later time points by using publicly available data sources as described in section 6.6.10 of the Protocol.

Table 8 Schedule of Activities – Cohort 2 (Platform Trial RGE Roll-over Participants)¹⁰

Activity	Screening/ Baseline Combined ^{1,8}	Week 3	Week 12	Week 24 or Early Term.	Follow-up Safety Call
	Clinic	Clinic	Telemed/ Phone	Clinic	Telemed/ Phone
	Day -21 to 0	Day 21 ±3	Day 84 ±7	Day 168 ±14	28 ±7 days after last doses
Written Informed Consent	X				
Inclusion/Exclusion Review	X				
ALS & Medical History	X				
Demographics	X				
Physical Examination ¹⁰	X				
Neurological Exam ¹⁰	X				
Vital Signs ²	X ^{1,10}	X Weekly documentation of infusion-associated vital signs			
Slow Vital Capacity (SVC) ¹⁰	X ¹	X			
ALSFRS-R	X ¹	X	X	X	
ALSAQ-40 ¹⁰	X ¹			X	
Clinical Safety Labs ³	X ¹	X		X	
Biomarker Collection (Serum) ¹⁰	X			X	
Concomitant Medication Review	X ¹	X	X	X	
Adverse Event Review	X ¹	X	X	X	X
Document infusion-related adverse events ⁴	X ¹	X Weekly documentation of infusion-related adverse events.			
Columbia-Suicide Severity Rating Scale	X ¹	X		X	
Adjust Dose as Needed ⁵		X			
Administer/Dispense Study Drug ⁶	X Weekly infusions will continue through Week 24. Participants who join from OLE may do all infusions at home.				
Drug Accountability/Compliance ⁷					

Activity	Screening/ Baseline Combined ^{1,8}	Week 3	Week 12	Week 24 or Early Term.	Follow-up Safety Call
	Clinic	Clinic	Telemed/ Phone	Clinic	Telemed/ Phone
	Day -21 to 0	Day 21 ±3	Day 84 ±7	Day 168 ±14	28 ±7 days after last doses
Vital Status Determination ⁹				X	X

1 Participants who join from HEALEY ALS Platform Trial Regimen E RCT and/or OLE may leverage assessments completed during the last Platform Trial visit if the last Platform Trial visit is completed on the same day as EAP Screening visit. Only those assessments collected after obtaining written informed consent for the EAP may be used in such cases.

2 Vital signs are collected at Screening/Baseline, Week 3, and Week 24 visits and weekly in conjunction with study drug administration from Baseline through Week 24. Vital signs collected at in-clinic visits (Screening/ Baseline, Week 3, Week 24) include weight, systolic and diastolic pressure, respiratory rate, heart rate, and temperature. Height is measured at Screening/Baseline Visit only. If significant weight change is reported or suspected at any point during the study, the SI may choose to collect an additional in-clinic weight at their discretion. During each weekly infusion, vital signs associated with the infusion (systolic and diastolic pressure, respiratory rate, and heart rate) are to be measured pre-infusion, 30 minutes (± 5 mins) after the start of infusion (SOI), 60 minutes after the SOI (± 10 mins), and 90 minutes (± 10 mins) after the SOI. If a participant requires a 90-minute infusion duration due to receiving more than 2 bags of study drug an additional vital signs measurement is to be completed approximately 30 minutes (± 10 mins) after the end of the 90-minute infusion.

3 Clinical safety labs include hematology (CBC with differential), complete chemistry panel and urinalysis at Screening/Baseline, Week 3, and Week 24. Hb A1C will be included in labs at Screening/Baseline and Week 24. If labs are abnormal at Week 3, they may need to be repeated per investigator judgement. Serum pregnancy testing will occur in women of child-bearing potential at the Screening Visit and as necessary during the study. Pregnancy testing is only repeated as applicable if there is a concern for pregnancy. All urine samples must be collected prior to IP administration. Clinical safety labs may be drawn at the study site or obtained at a local site convenient for the participant. Clinical safety lab results obtained locally may be used to assess participant eligibility.

4 Infusion-related AEs are documented weekly in conjunction with study drug administration from Screening/Baseline through week 24.

5 The weight collected at the Screening/ Baseline clinic visit will be used to calculate the participant's initial dose. The participant will remain on a stable dose until the next in-person visit when weight be collected, at which point the dose may be adjusted if the participant's weight has increased or decreased by 2kg. Additional information on dose adjustments is included in Protocol section 6.7.4 Dosing Changes.

6 Administer first dose of study drug only after Screening/Baseline Visit procedures are completed. For participants in cohort 2 who join from HEALEY ALS Platform Trial Regimen E OLE, all infusions may occur at-home. For participants in cohort 2 who join from HEALEY ALS Platform Trial Regimen E RCT, infusions occur in-person at clinic at the Screening/Baseline study visit, Week 1, Week 2, and the Week 3 study visits. Weekly infusions will continue through Week 24. An in-clinic infusion and clinic visit may occur on the same day, provided both visits are conducted in-person and within window. There should be no fewer than 4 days (96 hours) between study drug infusions.

7 Refer to the Pharmacy Manual, site policy, and GCP guidelines on site investigator responsibilities, drug accountability, compliance, and source documentation. Any and all accountability records may be requested by sponsor for review at any time.

8 The combined Screening/ Baseline visit may be split into a Screening and a Baseline visit as needed. If baseline infusion occurs on the same day as screening, it must occur after obtaining written informed consent, completing all screening procedures, and confirming participant eligibility.

9 Vital status, defined as a determination of date of death or death equivalent or date last known alive, will be determined for each enrolled participant at the end of their EAP participation (generally the Week 24 visit, as indicated). If at that time the participant is alive, his or her vital status should be determined again at the time of the last participant last visit (LPLV) of the EAP. We may also ascertain vital status at later time points by using publicly available data sources as described in section 6.6.10 of the Protocol.

Activity	Screening/ Baseline Combined ^{1,8}	Week 3	Week 12	Week 24 or Early Term.	Follow-up Safety Call
	Clinic	Clinic	Telemed/ Phone	Clinic	Telemed/ Phone
	Day -21 to 0	Day 21 ±3	Day 84 ±7	Day 168 ±14	28 ±7 days after last doses

10 Complete remote participation may be considered for select participants who join from HEALEY ALS Platform Trial Regimen E OLE on a case-by-case basis with permission from the Healey Coordination Center and Sponsor. Refer to Protocol section 6.2.1.

Appendix 2 Date Imputation Rules

The following rule will be used for missing/partial date imputation.

Item	Missing or Partial Date Variable	Imputation Rule
Adverse events, prior/concomitant medications and procedures	Start date	
The day is missing but month and year are available
 
 • If the month and year of occurrence are the same as month and year of the first study treatment, the start date will be set to the date of the first study treatment. • Otherwise, if the month and year of occurrence are not equal to the month and year of first study treatment, the start date will be set to the first day of the month of occurrence. 
The day and month are missing but year is available
 
 • If the year of occurrence is the same as the year of the first study treatment, the start date will be set to the date of the first study treatment. • Otherwise, if the year of occurrence is not the same as the year of the first study treatment, the start date will be set to January 1 of the year of occurrence. 
The start date is completely missing
 
 • The start date will not be imputed. • Adverse events will be considered treatment emergent unless the end date suggests otherwise. • Medications/Procedures will be considered both prior and concomitant unless the end date suggests otherwise. 
EXCEPTION: If complete end date is available and the imputed start date is greater than the end date, then the assumed start date should be set to the end date.

	End date	
The day is missing but month and year are available
 
 • If the participant died and the partial stop date is in the same month and year as the date of death, the end date will be set to the date of death. • Otherwise, the end date will be set to the last day of the month of occurrence. 
The day and month are missing but year is available
 
 • If the participant died and the partial end date is in the same year as the date of death, the end date will be set to the date of death. • Otherwise, the end date will be set to December 31 of the year of occurrence. 
The end date is completely missing
 
 • The end date will not be imputed.

		EXCEPTION: If the imputed end date is less than the start date, then the end date should be set to the start date.
ALS	Symptom onset date, diagnosis date	
The day is missing but month and year are available
 
• Impute the missing day to be 15. 
The day and month are missing but year is available
 
• Impute the missing month and day to be July 1. 
The date is completely missing
 
• The date will not be imputed.

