4.4.5 Medications, Therapies and Procedures

4.4.5.1 Prior and Concomitant Medications

Prior medications are medications and therapies with a start date before the first dose of study treatment. Concomitant medications are medications with a start date after the first dose of study treatment. Medications with a start date before the first dose of study treatment and with either an end date after the first dose of study treatment or are ongoing will be classified as both prior and concomitant medications. If a medication or therapy cannot be classified due to completely missing dates, it will be classified as both prior and concomitant.

Prior and concomitant therapies/medications will be summarized by ATC drug class (i.e., 4th level, or most specific level available if 4th level is unavailable) and preferred name for each treatment cohort and overall based on the FAS.

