4.9.2 Adverse Events

Participants will be monitored for adverse events from the time they sign consent for the EAP until completion of their participation as defined in the schedule of assessments.

Severity of AEs

Severity of AEs will be graded as Mild, Moderate, Severe. Missing grades will not be imputed, the AEs with missing grade will be summarized into the category of 'Not Reported' in the tabulation summary.

Relationship of AEs to Study Drug

The relationship of AE to study drug will be determined by Investigator. The relatedness categories include Related and Not Related.

TEAEs

AEs with the date of onset or worsening on or after the date of the first dose of study drug administration will be considered treatment emergent.

TEAEs Summary

AEs with onset after informed consent obtained but before the first dose of study drug will be collected but excluded from adverse event tabulations and presented in listing, only TEAEs are included in the summary by treatment cohort and overall for FAS. The number and percentage of participants with TEAEs will be presented for the summaries as described in **Table 6**. For table of overall summary, the number of events will also be provided.

Table 6 TEAE Summaries

Endpoint	Description
Overall summary	
 • TEAE • TEAE related to study drug • Serious TEAE

Endpoint	Description
	
 • Serious TEAE related study drug • Severe TEAE • Severe TEAE related study drug • TEAE leading to study drug dose reduced • TEAE leading to study drug interrupted • TEAE leading to study drug discontinuation • TEAE leading to early study discontinuation • TEAE leading to death (i.e., outcome is fatal)
TEAE	
 • Overall summary by SOC and PT • Overall summary by SOC, PT, and maximum severity grade • Overall summary by SOC, PT, and time to onset • Overall summary by PT
Most frequently-occurring ($\geq 5\%$) TEAE related to study drug	
 • Overall summary by PT
TEAE related to study drug	
 • Overall summary by SOC and PT • Overall summary by SOC, PT, and maximum severity grade • Overall summary by SOC, PT, and time to onset
Most frequently-occurring ($\geq 5\%$) TEAE related to study drug	
 • Overall summary by PT
Serious TEAE	
 • Overall summary by SOC and PT • Overall summary by SOC, PT, and time to onset

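### SAP Appendix 2 moves an item with a year-only start and a known pre-treatment stop month onto the first-dose day

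*SAP*

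**What the plan says.** One set of rules in SAP Appendix 2 covers "Adverse events, prior/concomitant medications and procedures". Four of its provisions matter here.

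- Year-only start in the first-dose year: the first-dose date is used ("If the year of occurrence is the same as the year of the first study treatment, the start date will be set to the date"). In any other year, "the start date will be set to January 1 of the year of occurrence".
- Start exception: "If complete end date is available and the imputed start date is greater than the end date", the start is set to the end date.
- End recorded as month and year: set to the last day of that month, or to the date of death if death falls in that month.
- End exception: "If the imputed end date is less than the start date, then the end date should be set to the start date".

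Where the start is entirely missing, the appendix imputes nothing and lets the end date decide whether the record belongs to treatment. The order in which start and end are imputed is not stated.

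SAP 4.1.3 says the imputation serves durations, treatment-emergent status and prior or concomitant status. It also says that listings still show the partial dates. The definitions that use the result are in SAP 4.4.5.1 ("Prior medications are medications and therapies with a start date before the first dose of study treatment"), in parallel wording for devices and procedures in 4.4.5.2, and in 4.9.2, where "AEs with the date of onset or worsening on or after the date of the first dose of study drug administration" are treatment-emergent.

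**The concern.** Some records show that an item stopped before treatment, because the stop month is known and lies wholly before first dose. Classification should respect that. Under the two exceptions taken together, the stop month is overwritten by a start date that was itself imputed. Whether the record is protected then depends only on whether someone wrote down the day of the stop.

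What is at stake is the class of the record. A drug, device or procedure that had ended can no longer meet the definition of prior use. An adverse event that ended during screening can enter the treatment-emergent tables, in the 0 to 12 week onset interval. The appendix also treats a record with more information (a known start year) worse than one with no start date at all.

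**Working it through.** The plan states no figure to reproduce. The check applies the Appendix 2 rules in sequence. The calendar dates are illustrative, since the documents give no individual records.

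**Medication, first dose 16 Oct 2023, start 2023 (year only), end Mar 2023.**

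1. The start year equals the first-dose year, so start = 16 Oct 2023.
2. The end has month and year, so end = 31 Mar 2023.
3. Start exception: the recorded end is not complete, so the start is not pulled back.
4. End exception: 31 Mar is before 16 Oct, so end = 16 Oct 2023.

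The result is 16 Oct to 16 Oct 2023. From 31 March, the latest possible stop, to 16 October is 30 + 31 + 30 + 31 + 31 + 30 (April to September) + 16 = 199 days. The start is no longer before first dose, so prior status is lost.

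**Same record, end 15 Mar 2023.** The end is complete, so the start exception applies. The result is 15 Mar to 15 Mar 2023, and prior status is kept.

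**Adverse event, first dose 5 Oct 2023, start 2023, end Sep 2023.** The same steps give 5 Oct to 5 Oct 2023, which is treatment-emergent under SAP 4.9.2. The latest possible stop, 30 September, is 5 days before first dose. The 21-day screening window (SAP 1.2) reaches back to 14 September, so such an event is possible.

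**Where the problem stops** (first dose 16 Oct 2023):

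| Recorded start | Recorded end | Result | Stop month kept? |
|---|---|---|---|
| 2023 | Mar 2023 | 16 Oct to 16 Oct 2023 | No |
| 2023 | 15 Mar 2023 | 15 Mar to 15 Mar 2023 | Yes |
| Feb 2023 | Mar 2023 | 1 Feb to 31 Mar 2023 | Yes |
| 2022 | Mar 2023 | 1 Jan 2022 to 31 Mar 2023 | Yes |
| Missing | Mar 2023 | Start not imputed; end decides | Yes |

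A January first dose cannot produce the conflict, because no earlier month exists in that year. The rules were also run with first dose on the 15th of each month of 2023, with start and end in the same calendar year, over year-only and month-and-year starts and over month-and-year and complete ends. Only a year-only start in the first-dose year with a month-and-year end before the first-dose month failed. The latest possible stop then lay 15 to 318 days before first dose.

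The reason is general. Ends are imputed to their latest possible day, so an imputed end can fall before the start only if the start was imputed too late or the recorded dates conflict.

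**The case against.** The best defence is that an end imputed to month end might count as a complete end date. If ends were imputed first and read that way, the example would give 31 Mar to 31 Mar 2023 and the problem would disappear. The appendix does leave the order open. Its vocabulary points the other way, however: it uses the word available for recorded date parts and speaks separately of an imputed end date. At the least, a programmer needs this settled.

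Setting an uncertain start to the first-dose date is also a familiar cautious convention. That holds when nothing else is known. It does not justify overriding a stop month that rules treatment out.

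Several stronger readings are tempting, and the documents do not support them.

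- *Every partial pre-treatment end date is unprotected.* The table above shows otherwise.
- *Adverse events that ended months before treatment become treatment-emergent.* Events are collected only from consent, with at most 21 planned screening days, and the AE log calls for onset and resolution dates (Protocol 10.4.4). Only an event that ended in the calendar month before first dose can be affected.
- *The ALS medication table is distorted.* SAP 4.4.1 identifies these drugs by preferred term from the concomitant medication form. It does not say that imputed dates decide use.
- *The record becomes concomitant.* SAP 4.4.5 defines concomitant by a start after first dose and does not place a start on that day. Protocol 6.6.4 counts receipt on or after Day 0. Only the loss of prior status follows directly from the SAP.
- *A given share of records is affected.* The documents give neither the number of such records nor the distribution of their stop months.

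**Conclusion.** Wrong as written, and minor. Read literally, Appendix 2 re-dates to the first-dose day any record with a year-only start in the first-dose year and a month-and-year end before the first-dose month. This overrides a stop known to precede treatment, by at least 199 days in the worked example, and removes prior status from a medication, device or procedure. For adverse events the route exists but should be rare.

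The conclusion rests on reading a complete end date as one recorded in full. The number of affected records is unknown and may be zero. On the text, only descriptive summaries change, and the partial dates remain visible in the listings.

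**What to change.** Make three changes in Appendix 2:

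1. State that end dates are imputed before start dates.
2. Reword the start exception: if the end date, whether complete or imputed to its latest possible day, is before the imputed start date, set the start date to that end date.
3. Restrict the end exception to records with a complete start date, so that an imputed start can never overwrite a known stop month.

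The medication example then becomes 31 Mar to 31 Mar 2023 and stays prior. The adverse event example becomes 30 Sep to 30 Sep 2023 and is not treatment-emergent. The complete-end record remains 15 Mar to 15 Mar 2023. Moving the start back to 1 January instead would not be a good repair: it could place an adverse event's onset before consent.

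The cost is two or three sentences and a small change to the date-imputation program, with no new data. One query on the date fields would show how many records are affected.
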